2. PATIENT POPULATIONS

The following patient populations will be evaluated and used for presentation and analysis of the data in this study, and for applicable analyses, relevant data from the APOLLO study.

- Modified Intent-to-Treat (mITT) Population: All randomized patients who received any amount of study drug. Patients will be analyzed according to the treatment to which they were randomized.
- TTR Per-protocol (PP) Population: All mITT population patients with a nonmissing TTR assessment at baseline and ≥ 1 trough TTR assessment between Months 6 (Week 24) and Month 18 [Week 72]) that meets the requirements described in [Table 3](#). Patients will be analyzed according to the treatment to which they were randomized.
- Month 9 Efficacy PP Population: All mITT population patients treated with vutrisiran or placebo meeting the following criteria:
 - Month 9 efficacy visit date within 3 calendar months of protocol-planned Month 9 efficacy visit window
 - No serious or severe COVID-19 custom query AE terms reported on or before Month 9 efficacy visit date
 - For vutrisiran-treated patients, received all planned vutrisiran doses up to and including Week 36 with ≤ 28 day delay

Patients will be analyzed according to the treatment to which they were randomized.

- Month 18 Efficacy PP Population: All mITT population patients treated with vutrisiran or placebo meeting the following criteria:
 - Month 18 efficacy visit date within 3 calendar months of protocol-planned Month 18 efficacy visit window
 - No serious or severe COVID-19 custom query AE terms reported on or before Month 18 efficacy visit date
 - For vutrisiran-treated patients, received all planned vutrisiran doses up to and including Week 72 with ≤ 28 day delay

Patients will be analyzed according to the treatment to which they were randomized.

- Cardiac Subpopulation: All mITT population patients who had preexisting evidence of cardiac amyloid involvement, defined as patients with baseline left ventricular (LV) wall thickness ≥ 1.3 cm and no aortic valve disease or hypertension in medical history. Patients will be analyzed according to the treatment to which they were randomized.
- Safety Population: All patients who received any amount of study drug. Patients will be analyzed according to the treatment received.
- Pharmacokinetic (PK) Population: All randomized patients who received at least one full dose of study drug and have at least 1 postdose blood sample for PK parameters

and have evaluable PK data. Patients will be analyzed according to the treatment received.

- All Vutrisiran-Treated Population: All randomized patients who received any amount of vutrisiran treatment, including patients who took vutrisiran during the 18-month treatment period and patients who first receive vutrisiran during the treatment extension periods.

■ [REDACTED]

For the 18-month Treatment Period, efficacy analyses (except TTR) and PD summaries will be conducted in the mITT Population unless otherwise specified. The noninferiority of TTR will be assessed using the TTR PP Population. Safety analyses will be conducted in the Safety Population. PK analyses will be conducted in the PK Population.

The All Vutrisiran-Treated Population will be used to summarize long-term safety data during vutrisiran treatment. [REDACTED]

Table 3: Postbaseline TTR Assessment Requirements by Treatment Group

Treatment Group	Postbaseline TTR Assessment Requirements
Vutrisiran or Patisiran	
• Assessment must be before administration of study drug at the current visit• Assessment after initiation of local standard treatment for hATTR amyloidosis excluded (Section 3.5)
Vutrisiran	
• Patient must receive planned, complete administration of study drug at the planned treatment visit approximately 12 weeks before the TTR assessment• Patient must receive planned, complete administration of study drug at 2 consecutive planned treatment visits at any time before the TTR assessment visit to ensure steady state
Patisiran	
• Patient must receive planned, complete administration of study drug at the planned treatment visit approximately 3 weeks before the TTR assessment

3. GENERAL CONSIDERATIONS

3.1. Computing Environment

All descriptive statistical analyses will be performed using SAS statistical software version 9.4 (or later), unless otherwise noted. Figures may be generated using R version 3.6 (or later).

3.2. General Methods

All data listings that contain an evaluation date will contain a study day relative to the day of the first dose of study drug, which is designated as Day 1. On-treatment study days will be calculated as evaluation date – first dose date +1 and pretreatment days will be calculated as evaluation date – first dose date. There is no Day 0.

Categorical descriptives will include the count and percentage of patients (or events, if applicable) within each category (with a category for missing data) of the parameter. Continuous descriptives will include the number of patients, mean, median, standard deviation (SD), standard error (SE), minimum, and maximum values.

Laboratory data (including vitamin A) collected and recorded as below the limit of detection will be set equal to the lower limit of detection for the calculation of summary statistics.

For assessments that are repeated multiple times for the study visit, the average will be calculated unless otherwise noted.

All summaries will be presented by treatment group. Unless otherwise specified, treatment groups in the Treatment Period will be presented using the following labels:

- Placebo (APOLLO)
 - Presented primarily for efficacy (except TTR) analyses and most safety and baseline summaries
- Vutrisiran (HELIOS-A)
- Patisiran (HELIOS-A)
- Total (HELIOS-A)
 - Presented primarily for patient disposition, protocol deviations, and baseline summaries

In addition, for TTR sensitivity analyses, the following treatment groups will be presented:

- Patisiran (HELIOS-A + APOLLO)
- Patisiran (APOLLO)

For analyses on the All Vutrisiran-Treated Population, the following treatment arms will be presented:

- Vutrisiran/Vutrisiran
- Patisiran/Vutrisiran
- Total

These 3 treatment arms represent the respective Vutrisiran (HELIOS-A), Patisiran (HELIOS-A), and Total (HELIOS-A) treatment groups, reflecting the transition from the initial randomized treatment (either vutrisiran or patisiran) during the Treatment Period to vutrisiran in the subsequent Legacy Treatment Extension or RTE periods. The experience while receiving vutrisiran will be summarized.

For analyses on the Re-randomized Population, the following treatment groups will be presented:

- Vutrisiran 25 mg q3M
- [REDACTED]
- Total

3.3. Baseline Definitions

Baseline definitions will be defined separately for analyses in the 18-Month Treatment Period, during vutrisiran treatment (ie, All Vutrisiran-Treated Population), and the 18-Month Randomized Treatment Extension Period (ie, Re-randomized Population).

3.3.1. 18-Month Treatment Period Analyses

For the mNIS+7/NIS individual components, total scores and related endpoints, the 2 baseline assessments are performed on separate days. Baseline will be calculated as the mean of the nonmissing replicate measures.

For 10-MWT, 2 baseline assessments are performed on separate days. Baseline will be calculated as described in Section 9.1.4.

For PD parameters (TTR, Vitamin A), baseline will be defined as the average of all records, including those from any unscheduled visits, before the date and time of first dose.

For all other parameters, unless noted otherwise, baseline will be defined as the last nonmissing measurement on or before the first dose date.

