3.3.3. Re-randomized Population Analyses

For the mNIS+7/NIS individual components, total scores, and related endpoints, and 10-MWT, baseline will be defined as the last nonmissing derived value before the first dose in the RTE Period. In most cases, this will correspond to the Month 18 derived values.

For all other efficacy and all safety parameters, unless noted otherwise, baseline will be defined as the last nonmissing measurement before the first dose in the RTE Period.

Baseline ADA status will be defined as the last nonmissing anti-TTRSC02 ADA assay measurement before the first dose in the RTE Period. In most cases, this will correspond to the RTE Day 1 measurement.

For PD parameters (TTR, Vitamin A), baseline will be defined the same as for the 18-Month Treatment Period (Section 3.3.1).

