3.7. Visit Windows

It is expected that all visits should occur according to the protocol schedule. All data will be tabulated and analyzed per the evaluation visit as recorded on the electronic case report form (eCRF) even if the assessment is outside of the visit window.

For efficacy assessments, if the scheduled visit (eg, Month 9) is not performed, the unscheduled and/or discontinuation visits performed within a ± 3 -month window will be grouped with the scheduled visit. In situations in which a Month 9 or Month 18 efficacy visit is unable to be completed due to the Coronavirus disease 2019 (COVID-19) pandemic limiting the patient’s ability or willingness to access the study center or their ability to have received their scheduled

doses of study drug, Month 9 and Month 18 efficacy assessments may be completed within 6 months after the intended time point (ie, up to Study Month 15 or Month 24, respectively). For patients impacted by the COVID-19 pandemic, efficacy visits delayed up to 6 months after the end of the protocol-defined efficacy visit window will be included in the analysis. The derived visits will be used for all analyses. [REDACTED]

Unless otherwise specified above, data collected at unscheduled visits will be included in by-patient data listings and figures, but no assignment to a study visit will be made for the purpose of by-visit summary tabulations. However, unscheduled visits may be used in the calculation of baseline values (as discussed in Section 3.3) and for inclusion in any categorical shift summaries (e.g., shift from baseline to “worst” postbaseline value).

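### The default baseline rule in SAP Section 3.3.1 stops at the first dose date, not at the dose, so a laboratory or vital-sign value taken after dosing on Day 1 can become baseline

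*SAP*

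**What the plan says.** All references are to the current SAP, Amendment 3.

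- **Default rule, Section 3.3.1:** "For all other parameters, unless noted otherwise, baseline will be defined as the last nonmissing measurement on or before the first dose date".
- **Day 1, Section 3.2:** study day is counted from "the day of the first dose of study drug, which is designated as Day 1". The first dose date therefore includes the hours after dosing.
- **Pharmacodynamic rule for TTR and vitamin A, Section 3.3.1:** "baseline will be defined as the average of all records, including those from any unscheduled visits, before the date and time of first dose".
- **RTE rule, Section 3.3.3 (other efficacy and all safety parameters):** "baseline will be defined as the last nonmissing measurement before the first dose in the RTE Period".
- **Parameters with other rules of their own:** for mNIS+7 and NIS, "Baseline will be calculated as the mean of the nonmissing replicate measures"; 10-MWT follows Section 9.1.4; ECG uses the average of the baseline triplicate (Section 4.7.5).
- **Unscheduled values, Section 3.7:** "However, unscheduled visits may be used in the calculation of" baseline values, with a cross-reference to Section 3.3.
- **Repeats, Section 3.2:** assessments repeated within a study visit are averaged unless the plan says otherwise.

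**The concern.** A baseline should describe the patient before treatment. A rule that takes the last value up to the end of the dosing day does not guarantee that. If a blood sample or vital sign is repeated after the first dose on Day 1, the later reading meets the definition and the predose one is passed over.

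Two things then go wrong. The post-dose reading becomes the reference and is no longer available as a postbaseline value, so an early abnormality can be missing from worst-value summaries. Every later change is also measured from a value that may already reflect the drug, the premedication or a reaction.

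The outputs at stake are descriptive. Section 4.7.3 plans laboratory changes and percent changes from baseline by visit, together with shifts to the worst value for ALT, AST, total bilirubin and eGFR. Section 6.2 plans shift summaries for laboratory and vital-sign parameters during vutrisiran treatment, and Section 3.3.2 gives these the Section 3.3.1 baseline.

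**Working it through.** The plan gives no figure for this point, so the check is a comparison of its rules followed by the arithmetic of a contaminated baseline.

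**1. Is there a predose limit on the default?**

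| Rule | Limit | Can a post-dose Day 1 value enter? |
|---|---|---|
| Default, 3.3.1 | first dose date | Yes |
| TTR and vitamin A, 3.3.1 | date and time of first dose | No |
| RTE Period safety and other efficacy, 3.3.3 | before the first RTE dose | No |

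No predose condition on the default appears in Section 3.2, 3.3, 3.7, 4.7.3 or 4.7.4. One cannot safely be read in, because the neighbouring pharmacodynamic sentence states a time limit explicitly. The same safety parameter thus has a strict baseline in the RTE analysis and a date-only one in the 18-month analysis.

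**2. What does the default govern?** Removing mNIS+7, NIS, 10-MWT, TTR, vitamin A and ECG leaves laboratory tests and vital signs. Formally it also leaves Norfolk QoL-DN, mBMI, R-ODS, EQ-5D-5L, cardiac biomarkers, echocardiography, the clinical staging scales and C-SSRS. A same-day repeat after dosing is unlikely for questionnaires, echocardiography and staging, so the practical reach is mainly laboratory and vital-sign values.

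**3. Size of the error in an affected patient.** Let B be the predose value, P a Day 1 post-dose value, d = P − B, and Y a later value.

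- Predose baseline: change = Y − B, and P counts as postbaseline with change d.
- Last value on Day 1: change = Y − P = (Y − B) − d, and P is not postbaseline.
- Mean of the two Day 1 values: change = Y − (B + P)/2 = (Y − B) − d/2.

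Illustration with assumed systolic pressures, not taken from the SAP: B = 130, P = 88, Y = 128, so d = 88 − 130 = −42.

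| Baseline used | Baseline | Change at P | Change at Y |
|---|---|---|---|
| Predose | 130 | −42 | 128 − 130 = −2 |
| Last on Day 1 | 88 | not counted | 128 − 88 = +40 |
| Mean on Day 1 | (130 + 88)/2 = 109 | not counted | 128 − 109 = +19 |

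The algebra is the same for a laboratory value of any size.

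**4. How many patients?** This needs the Day 1 schedule for laboratory tests and vital signs, which the SAP leaves to the protocol. The post-dose Day 1 samples that the SAP does describe are pharmacokinetic (Section 4.6.1.2), and concentrations are not change-from-baseline parameters.

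**The case against.** The strongest reply is that the trigger is not shown. If all Day 1 laboratory and vital-sign assessments come before dosing, the rule does no harm. That stands as a limit on frequency, but it does not supply the missing predose condition.

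Second, the permission in Section 3.7 points back to Section 3.3, where only the pharmacodynamic rule mentions unscheduled records, and that rule is already time-bounded. So it is not settled that an unscheduled Day 1 reading may enter the default baseline. Nothing excludes it, however, and the default admits any scheduled post-dose value without relying on Section 3.7.

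Third, the averaging in Section 3.2 may apply. With two readings it would halve the error, as shown above, but not remove it.

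A reader might go further and infer three things that the document does not support:

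- **That first-infusion reactions are hidden, or that the vutrisiran–patisiran safety comparison is distorted.** Section 4.7.2 counts adverse events from the start of administration and tabulates and lists infusion-related reactions. Section 4.7.1 tabulates infusion interruptions due to them. None of this uses a baseline value. For the 18-month period, Section 4.7.4 names no baseline-to-worst shift for vital signs. The vital-sign shifts in Section 6.2 exclude data collected on patisiran in the Treatment Period.
- **That efficacy results are at risk.** The primary endpoint has its own rule, and no efficacy consequence can be shown from the text.
- **That a particular number of patients is affected.** Assuming 5% to 25% of about 40 patisiran patients (160 × 1/4) would give 2 to 10, but that share has no source in the SAP.

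**Conclusion.** The point holds in a limited form. The default baseline rule admits post-dose Day 1 values and is looser than the plan's own pharmacodynamic and RTE rules. For an affected patient, later changes are off by the full predose-to-postdose difference, or by half of it if two readings are averaged, and the post-dose value leaves the postbaseline set. The consequence falls mainly on descriptive laboratory summaries, including the ALT, AST, bilirubin and eGFR shifts, and on vital-sign summaries.

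This rests on one condition that the SAP neither confirms nor excludes: that some laboratory or vital-sign value is recorded after dosing on Day 1. The frequency is unknown. mNIS+7, NIS, 10-MWT, TTR, vitamin A, ECG and the adverse event and infusion-reaction tables are untouched. The change is worth making because the wording is wrong as it stands and cheap to correct.

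**What to change.** Reword the default in Section 3.3.1 along these lines: *baseline is the latest nonmissing value obtained before the first dose, judged by date and time; where no time is recorded, a Day 1 value is used only if it was scheduled or labelled as predose; any Day 1 value obtained after dosing is treated as postbaseline.* State that this takes precedence over the within-visit averaging in Section 3.2. Section 3.3.2 then inherits the correction.

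This borrows the predose limit already used for the pharmacodynamic and RTE baselines. It does not adopt the averaging of all predose records in the pharmacodynamic rule, and the provision for untimed values is new.

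The cost is a sentence or two of SAP text and a matching change in the derivation program. The SAP does not show whether collection times or predose labels exist for vital signs and laboratory tests, so confirm that against the case report form and laboratory data before finalising the wording.

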3.3.2. All Vutrisiran-Treated Population Analyses

For patients in the Patisiran/Vutrisiran arm, baseline ADA status will be defined as the last nonmissing anti-TTRSC02 ADA assay measurement before the first vutrisiran dose in the extension periods. In most cases, this will correspond to either the Month 18 or Week 72 measurement.

For all other parameters, unless noted otherwise, baseline will be defined the same as for the 18-Month Treatment Period (Section 3.3.1).

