6.2. During Vutrisiran Treatment

Data in the vutrisiran-treatment period will consist of all data on or after the first administration of vutrisiran treatment:

- For patients randomized to vutrisiran, all data in the Treatment and Treatment Extension periods will be included
- For patients randomized to patisiran, all data in the Treatment Extension periods will be included; data in the Treatment Period while on patisiran treatment will be excluded

Where applicable, baseline will be defined as described in Section 3.3.2. Summaries will be presented by vutrisiran/vutrisiran, patisiran/vutrisiran, and overall, and will be based on the All Vutrisiran-Treated Population.

Duration of drug exposure will be defined as last vutrisiran date – first vutrisiran dose date + 1, with last vutrisiran date during vutrisiran treatment defined as the earliest of the following dates:

- Last vutrisiran dose date + treatment-specific window (83 days if last vutrisiran dose received is [REDACTED]; 167 days if last dose received is [REDACTED])
- Analysis cutoff date
- End of study date

AE and ISR summaries described in Section 4.7.2 will be provided for vutrisiran-emergent adverse events, defined as treatment-emergent adverse events occurring on or after the first dose of vutrisiran treatment through a treatment-specific window following the last dose of vutrisiran (84 days if last vutrisiran dose received is [REDACTED]; 168 days if last dose received is [REDACTED]). Potentially clinically significant postbaseline abnormalities and shift from baseline to the worst postbaseline status for laboratory, vital signs, and ECG parameters, ADA, concomitant medications, and overall study drug exposure, during the vutrisiran-treatment period will be summarized.

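### On-vutrisiran shift tables for laboratory, vital-sign and ECG parameters use a pre-patisiran baseline for patients who crossed over from patisiran

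*SAP*

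**What the plan says.** All references are to the current SAP, Amendment 3.

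- **Purpose.** Section 3.2 sets up three columns for the All Vutrisiran-Treated Population (Vutrisiran/Vutrisiran, Patisiran/Vutrisiran, Total) and says of them: "The experience while receiving vutrisiran will be summarized".
- **Data window.** For patients first randomised to patisiran, Section 6.2 keeps only extension-period data and excludes what was collected on patisiran.
- **Tables concerned.** Section 6.2 includes among its summaries the "shift from baseline to the worst postbaseline status for laboratory, vital signs, and ECG parameters".
- **Baseline.** Section 6.2 points back: "Where applicable, baseline will be defined as described in Section 3.3.2". Section 3.3.2 makes one exception for the crossover arm, namely that "baseline ADA status will be defined as the last nonmissing anti-TTRSC02 ADA assay measurement before the first vutrisiran dose in the extension periods". Everything else follows this rule: "For all other parameters, unless noted otherwise, baseline will be defined the same as for the 18-Month Treatment Period".
- **What that baseline is.** In Section 3.3.1, for parameters without their own rule, "baseline will be defined as the last nonmissing measurement on or before the first dose date". Section 4.7.5 averages the baseline triplicate ECGs and names no second baseline.
- **Contrast.** For all safety parameters in the Re-randomized Population, Section 3.3.3 says "baseline will be defined as the last nonmissing measurement before the first dose in the RTE Period".

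**The concern.** In Section 6.2 the data window and the reference point do not match. The window opens at the first vutrisiran dose. For the crossover arm, the reference value dates from before a full period on another drug. Whatever developed in between and persists, whether from the disease, from patisiran or from its premedication, is read as something that happened on vutrisiran. The error can also run the other way and hide a recurrence on vutrisiran.

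At stake is the reading of the long-term safety tables for vutrisiran after patisiran, and of the Total column, which would combine two different reference points. No efficacy test, endpoint or alpha allocation depends on this.

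**Working it through.** **1. Which first dose is meant.** Section 3.2 counts the "study day relative to the day of the first dose of study drug, which is designated as Day 1". For the patisiran arm, Day 1 is the first patisiran dose. Section 3.3.2 names the first vutrisiran dose only for ADA and sets all other parameters apart from it. Reading the Section 3.3.1 baseline as the last value before vutrisiran is therefore not open for this arm.

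**2. What the rule does to a shift table.** N = normal, A = abnormal. The fourth column is the SAP's rule (study entry to worst value on vutrisiran). The fifth takes baseline at the switch.

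| Study entry | At switch | Worst on vutrisiran | Worsening shown by SAP rule | Worsening from switch |
|---|---|---|---|---|
| N | A | A | yes | no |
| A | N | A | no | yes |
| N | A | N | no | no |
| N | N | A | yes | yes |
| A | A | A | no | no |

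The first row is a shift wrongly placed in the vutrisiran period. The second is a worsening on vutrisiran that is lost. The third shows the limit: a patisiran-period change that has gone by the time of the extension assessments is not counted, because on-patisiran data are excluded.

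A constructed example using the eGFR bands of Section 4.7.3: values of 65 at entry, 55 at the switch and 55 throughout vutrisiran are tabulated as a fall from the ≥60 to <90 band to the ≥45 to <60 band, although nothing changed on vutrisiran.

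**3. How many patients.** Section 1.4 plans about 160 patients at 3:1.

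- Patisiran arm: 160 × 1/4 = 40
- Share of the Total column if all cross over: 40/160 = 25%

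**4. Age of the baseline at the switch.** Section 4.7.1 places the start of the Legacy Treatment Extension at Week 84: 84 × 7 = 588 days, and 588/30.4375 = 19.3 months. For patients entering the randomised extension directly, the switch follows the 18-month Treatment Period.

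**5. Possible effect on the tables.** The SAP gives no figure for how many patients would carry a change across the switch. Let q be the share of crossover patients whose abnormality arose on patisiran and persists. This is an assumption, shown as a range. Misplaced shifts = 40q; the crossover column rises by q; the Total column rises by 40q/160.

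| q | Patients | Crossover column | Total column |
|---|---|---|---|
| 5% | 2 | +5 points | +1.25 points |
| 10% | 4 | +10 points | +2.5 points |
| 20% | 8 | +20 points | +5.0 points |

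The SAP states no figure that depends on this rule, so there is none to reproduce.

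**The case against.** The strongest defence is that the rule is an explicit choice. Section 3.3 says baselines differ by analysis, and the study-entry value gives both arms a common untreated reference. ADA is a special case, since an anti-vutrisiran antibody baseline makes sense only before vutrisiran. The summaries are descriptive and the arms are shown separately, so a reader can set the crossover column aside. The Re-randomized tables, which do reset the safety baseline, may fill part of the gap.

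Some of this stands. The tables are descriptive, the Vutrisiran/Vutrisiran column is sound, and the ADA rule alone proves no inconsistency. The rest is weaker. The SAP nowhere gives a common untreated reference as its reason, and Section 3.3.3 takes the opposite course for all safety parameters when a new period starts. Section 5 is redacted, so the extent of any overlap cannot be seen. In any case, a patient who switched in the Legacy extension and entered the randomised extension later would be re-baselined after vutrisiran had begun. Long-term change from study entry already has a place in the over-time summaries of Section 6.

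A reader might infer three stronger things that the document does not support:

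- **Every change on patisiran is charged to vutrisiran.** Only those still present at an extension-period assessment are.
- **Counts of large QTc increases are distorted.** Those categories are in Section 4.7.5, for the 18-month period; Section 6.2 does not name them.
- **Counts of potentially clinically significant abnormalities are distorted.** The SAP shows no criteria for them. If they are absolute thresholds, baseline plays no part.

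**Conclusion.** The point holds for the baseline-to-worst shift tables of laboratory, vital-sign and ECG parameters in Section 6.2. It affects the Patisiran/Vutrisiran column and the Total column only. Vutrisiran-emergent adverse events are defined by onset on or after the first vutrisiran dose, and ADA is re-baselined, so neither is affected.

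Forty of 160 is an upper bound on the patients exposed to the rule: it assumes planned enrolment and that every patisiran patient crosses over. It should not be read as 40 misclassified patients. The 2 to 8 in the working rest entirely on the assumed q of 5% to 20%. The change should be made because these tables are meant to describe the time on vutrisiran and, for one arm, do not. No efficacy conclusion is in question.

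**What to change.** Add one sentence to Section 3.3.2: for the Patisiran/Vutrisiran arm, baseline for laboratory, vital-sign and ECG shift-from-baseline summaries, and for any other change-from-baseline safety category presented for this population, is the last nonmissing value before the first vutrisiran dose. Keep the study-entry baseline for TTR and vitamin A, where percent reduction needs an untreated reference.

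The cost is that sentence and a second baseline flag in the safety datasets. The one drawback is that this arm's baseline in the Section 6.2 tables will differ from that in the whole-study by-visit tables. A footnote on each deals with it, and shifts from the study-entry baseline can be kept as a supplementary display.
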